3.3 Analysis of the Secondary Endpoints

The three secondary endpoints are:

- i. Recurrent events of the primary composite endpoint
- ii. All-cause mortality
- iii. Composite of cardiovascular mortality, MI, or stroke

3.3.1 Recurrent-event analysis of the primary endpoint

Recurrent event analyses include all positively adjudicated primary endpoint events attributed to a participant: all-cause mortality, recurrent MI, stroke, coronary revascularization, or hospitalization for unstable angina events. The number of patients with a primary composite endpoint and the frequency of the primary composite endpoint per each component will be

summarized by active chelation and placebo. We analyze this endpoint using two statistical techniques:

- i. The generalization of the Cox model to handle recurrent events developed by Andersen & Gill (1982) is the most frequently used approach to estimate treatment differences with total and recurrent events. This approach models gap time (time from enrollment to first event or from one event to the next) and assumes independence of observed event times within the same subject with the adjustment of the covariates. Our modeling will use robust standard errors to account for individual patients' heterogeneity and covariance across event times. The treatment effect will be presented as a hazard ratio (EDTA vs. placebo) and associated 95% CIs and *P*-value. It will be the primary analysis for the total number of all-cause mortality, recurrent MI, stroke, coronary revascularization, or hospitalization for unstable angina events endpoint.
- ii. The stratified marginal Cox modeling approach developed by Wei, Lin, and Weissfeld (WLW) (1989) considers each event recurrence separately and models all the available data for the specific event. Therefore, each subject is considered to be at risk for all events, regardless of how many events each subject actually experienced. A different baseline hazard function is assumed for each event, through use of strata for each event. The WLW will model the marginal hazard of each event's failure time. The time interval for each event for each subject starts at date of randomization and ends at the time of the specific event or censoring. A treatment effect will be presented as a hazard ratio (EDTA vs. placebo) and a 95% CI and *P*-value. This will be considered as a sensitivity analysis.

Both analyses will be adjusted for age, sex, and baseline insulin use. In either analysis, a hazard ratio of < 1 would suggest a benefit for the chelation-based therapy.

An event rate of the endpoint for each treatment group will be calculated as percentage per 100 patient years, accounting for differential follow-up duration. A 95% CI for the event rates will be calculated as

$$\left(\frac{r_c}{T_c} \right) \pm 1.96 \sqrt{\frac{r_c}{T_c^2}}$$

where subscript *C* denotes the chelation arm, and *r* is the total number of event occurrences, and *T* is the total follow-up time among all participants.

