3.1 General

3.1.1 Estimands and Censoring Scheme

Summaries of the descriptions of the estimand attributes and censoring schemes are shown in **Table 3**. Like TACT, the primary analysis will include all identified events obtained as part of the planned follow-up from infusion visits and call center interviews.

Table 3. Key Study Estimands and Censoring Scheme.

Objective Description / Study Population	Endpoint	Summary statistics	Events to be included in the endpoint derivation	Censoring date
Primary Objective/ mITT	Time from randomization to the first occurrence of primary composite endpoint of all-cause mortality, MI, stroke, coronary revascularization, or hospitalization for unstable angina	Hazard ratio estimate based on a Cox proportional hazards model.	All positively adjudicated primary endpoint events post-randomization except those occurring after withdrawal of consent or ICF expiration. Events occurring after withdrawal consent or ICF expiration will be censored. Subjects with events after withdrawal or ICF expiration will be censored at the min(date withdrew consent, date of last contact with patient/proxy where event status was assessed).	Among subjects not experiencing endpoint of interest: Censoring date = min(date withdrew consent, date of last contact with patient/proxy where event status was assessed) Date of last contact defined as: If the last contact occurred during the study infusion phase - use last infusion visit date where survival status and event status were assessed (yes or no to event). If last contact occurred during call center follow up period – use ‘complete’/‘incomplete’ status date by patient/proxy where survival status and hospitalization status were assessed (yes or no to hospitalization).

				For composite endpoints, date of last assessment = the earliest of the last assessment date among all components.
Secondary Objective / mITT	Overall rate of recurrent events due to all-cause mortality, MI, stroke, coronary revascularization, or hospitalization for unstable angina	Hazard ratio estimate based on a proportional intensity model by Andersen-Gill and a marginal model by Wei, Lin and Weissfeld.	*same as primary endpoint	*same as primary endpoint

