3.2 Primary Endpoint Analysis

The primary endpoint is the composite of all-cause mortality, MI, stroke, coronary revascularization, or hospitalization for unstable angina.

If two of the component events of the primary composite endpoint occur on the same day, the following hierarchy will be used when reporting the components of the primary endpoint. For example, a patient with stroke and all-cause mortality on the same date will be considered as having stroke when summarizing individual events within the primary composite outcome. This hierarchy will only be used for summarizing events within the primary composite outcome and will not affect the primary analysis.

- i. MI
- ii. Stroke
- iii. Hospitalization for unstable angina
- iv. Coronary revascularization
- v. All-cause mortality

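### SAP 3.3.1: the confidence interval for each arm's total-event rate is Poisson and ignores clustering of events within participants; the Andersen-Gill time scale also needs reconciling

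*SAP*

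**What the plan says.** SAP 3.3.1 defines the total-events endpoint broadly: "Recurrent event analyses include all positively adjudicated primary endpoint events attributed to a participant". One participant can therefore contribute several events.

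Each treatment group gets a rate per patient-time, and "A 95% CI for the event rates will be calculated as" r/T ± 1.96·√(r/T²). In this formula r "is the total number of event occurrences" and T is the total follow-up time. Only the chelation subscript is defined, but the text applies the rate to each group.

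For the hazard ratio, the same section adds a safeguard: "Our modeling will use robust standard errors to account for individual patients' heterogeneity and covariance across event times". No such allowance is attached to the rate interval.

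SAP 3.2 has a tie rule that begins "If two of the component events of the primary composite endpoint occur on the same day" and gives stroke with death as its example. Its scope is limited: "This hierarchy will only be used for summarizing events within the primary composite outcome and will not affect the primary analysis". Nothing says whether a same-day pair counts once or twice in r.

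On the model, SAP 3.3.1(i) names Andersen and Gill and then says: "This approach models gap time (time from enrollment to first event or from one event to the next) and assumes independence". Table 3 in SAP 3.1.1 describes the same analysis as "Hazard ratio estimate based on a proportional intensity model by Andersen-Gill". The paper cited in SAP section 4 is titled as a regression model for counting processes. The protocol (section 9.6) mentions a generalized Cox model with robust standard errors and states no time scale.

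**The concern.** The formula sets the variance of r equal to r. That holds when occurrences arise independently at a common rate. It fails if some participants are more event-prone than others, or if one clinical episode yields two counted components, such as a myocardial infarction followed by revascularization. The SAP accepts the first possibility when it chooses robust standard errors for the model, and its tie rule provides for the second. In either case the printed intervals for the arm rates would be too narrow and would overstate precision.

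The time-scale point is separate and smaller. Andersen-Gill as usually defined runs on time since randomization with (start, stop] intervals; restarting the clock after each event is a different model. Two programmers could read the section and fit different models. This is the model tested at step 4, the last step of the hierarchy in SAP 3.2.1.

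**Working it through.** **Algebra of the formula.** √(r/T²) = √r/T, which is exactly the Poisson standard error of r/T. The documents give no r, T, total-event rate, dispersion or fatal share for TACT2, so there is no planned figure to reproduce.

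**Closed form.** Let participants' rates vary by a gamma frailty with mean 1 and variance θ around a total-event rate λ, with follow-up t. Then

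Var(r)/E(r) = 1 + θ·λ·E(t²)/E(t), and formula coverage = 2Φ(1.96/√inflation) − 1.

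Assume t uniform on 2.5 to 5 years. E(t) = 3.75, E(t²) = (6.25 + 12.5 + 25)/3 = 14.58, and the ratio is 3.89. With λ = 0.10 and θ = 1 (both assumed), inflation = 1 + 0.389 = 1.39, the standard-error ratio is √1.39 = 1.18 and coverage is 90.4%. Over λ = 0.10-0.20 and θ = 0.5-2, the ratio runs from 1.09 to 1.60 and coverage from about 93% to 78%. This version does not let death end follow-up.

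Paired events have the same effect without frailty. If an episode adds a second counted component with probability p, inflation = (1 + 3p)/(1 + p). At p = 0.3 this is 1.9/1.3 = 1.46, a ratio of 1.21 and coverage of 89.5%.

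**Simulation tied to the plan's rates.**

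- From the documents: 500 per arm (1000 enrolled) and first-event rates of 7.2 (chelation) and 10.4 (placebo) per 100 patient-years (SAP Table 2 and Appendix I).
- Assumed: follow-up uniform on 2.5-5 years; each event fatal with probability 0.25 or 0.40, ending follow-up; θ = 0.5, 1 or 2. Each non-fatal event is counted twice with probability 0, 0.1 or 0.3.
- The base rate was solved to match the first-event rate: 0.076, 0.082 and 0.094 per year (chelation) and 0.114, 0.126 and 0.152 (placebo) for θ = 0.5, 1 and 2.
- There were 6,000 replicates per setting; simulation error on coverage is 0.3-0.5 points.

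| Setting | True SE ÷ formula SE | Formula coverage |
|---|---|---|
| No frailty, no pairs | not tabulated | 94.5-95.2% |
| Frailty only, chelation | 1.04-1.19 | 89.3-94.0% |
| Frailty only, placebo | 1.05-1.30 | 86.5-93.8% |
| 10% pairs only | not tabulated | 93.2-93.6% |
| 30% pairs only | not tabulated | 90.4-91.9% |
| Frailty and 30% pairs | not tabulated | 79.6-90.0% |

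Example with θ = 1 and 25% fatal: chelation 7.9 ± 1.30 per 100 patient-years should be ± 1.43 (ratio 1.43/1.30 = 1.10). Placebo 11.9 ± 1.61 should be ± 1.85 (1.85/1.61 = 1.15).

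The patient-clustered alternative, SE = √[Σᵢ(nᵢ − (r/T)tᵢ)²]/T with nᵢ events and tᵢ follow-up for participant i, covers 94.2-95.3% in every setting.

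**Time scale.** There were 1,500 trials per setting, with 2 × 500 participants, a placebo first-event rate of 10.4, 25% of events fatal and θ = 0, 1 or 2. An unadjusted Cox model with patient-clustered robust standard errors was fitted to the same data on both scales. At a true hazard ratio of 0.7, mean gap-time HR minus mean total-time HR was:

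- 0.000-0.009 with constant intensity;
- 0.008-0.014 with Weibull shape 0.7;
- 0.013-0.018 with Weibull shape 0.5 (for example 0.739 against 0.721).

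Under the null, rejection was 4.1-6.7% (total time) and 3.9-6.5% (gap time), with simulation error of about 0.6 points. The verdict differed in at most 1.7% of trials.

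**The case against.** The rate interval is descriptive. No test or decision depends on it, and the inferential analysis already has robust standard errors. A crude rate with a Poisson interval is a common summary. All of that stands, and it is why the point is minor. It does not make the interval correct under the heterogeneity that the SAP itself allows for.

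The size rests wholly on assumed dispersion, fatal share and pairing. The two calculations above also differ (ratios of 1.04-1.30 against 1.09-1.60), because the closed form assumes higher total-event rates and no truncation by death. This stands too: only the direction is firm. The 79.6% figure combines strong frailty with the highest assumed pairing rate and should not drive the grading.

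The tie rule is conditional and does not predict many pairs, and its stroke-with-death example is not covered by a simulation that doubles non-fatal events only. Pairing also moves the rate itself. With 25% fatal and 30% of non-fatal events doubled, the chelation rate rises from 7.2 to 7.2 × (1 + 0.75 × 0.30) = 8.8 per 100 patient-years, or 22%. A clustered interval is valid under either counting rule but does not choose between them, so r still needs a definition.

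On gap time, no other passage states a different clock, and the model can be programmed as written. The conflict is between the name as usually understood and the description. That part is a wording reconciliation and would not merit a comment on its own.

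**Conclusion.** The concern holds as a minor point. The interval in SAP 3.3.1 is too narrow whenever events cluster within participants. The direction follows from the formula; the size depends on dispersion that the documents do not give. With the plan's first-event rates and the assumed frailty and fatal share, the nominal 95% intervals cover about 86.5-94.0% before any double counting. If events do not cluster, the formula is adequate. The treatment hazard ratio, its interval and its P-value do not depend on this formula.

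The gap-time description does not match the usual meaning of the model's name. The simulated consequence is a hazard-ratio shift of up to about 0.02 at the last step of the hierarchy.

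**What to change.** 1. In SAP 3.3.1, replace the interval in each arm with a patient-clustered one: the sandwich standard error given above, or a bootstrap that resamples participants. A negative-binomial interval is an alternative, but it was not simulated here. Define r and T for both arms, and state whether same-day components count as one event or several. The interval change costs one sentence and about one line of code. Reported intervals widen by 4-30% under the assumed frailty without pairs, and not at all if events do not cluster. The hazard-ratio analysis is untouched.

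2. Before unblinding, reconcile SAP 3.3.1(i). Either specify (start, stop] time since randomization with patient-clustered robust standard errors, or keep gap time and rename the model. This is one wording edit. If it changes the programmed time scale, the step 4 result can move slightly, so it must be settled without sight of treatment results.

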3.3.2 Time to Event Analysis of the Secondary Endpoints

The analyses for the time to the first occurrence of secondary endpoints (1) time to the first occurrence of the composite of cardiovascular mortality, MI, or stroke; 2) time to all-cause

mortality) will be performed in the same manner as the primary analysis in Section 4.1, replacing the primary composite endpoint with secondary endpoints.

Competing risk of non-CV death or undetermined death will be taken into account for the secondary composite endpoint (time to the first occurrence of the composite of cardiovascular mortality, MI, or stroke). Follow-up will be censored at the time of non-CV or undetermined death if there is no prior composite event. For this endpoint, the treatment effect will be presented as a cause-specific hazard ratio.

All deaths post-randomization will be included in the secondary all-cause mortality endpoint. For this endpoint, a death date after withdrawal of consent or ICF expiration (obtained from public data sources) is considered an event.

3.3.3 Sensitivity Analyses of the Secondary Outcomes

A sensitivity analysis is planned for the secondary composite endpoint where undetermined death will be classified as CV-death.

Another sensitivity analysis is planned for the secondary composite endpoint where cause of death is determined based on the best available data. Cause of death will first be determined based on the data from the CEC. If cause of death from the CEC is unavailable, cause of death will be determined from the CRF data. If cause of death from the CEC and CRF is unavailable, cause of death will be determined based on the NDI data.

A sensitivity analysis is planned for the secondary all-cause mortality endpoint where participants with no event will be censored at the last date that NDI results were assessed. The censoring date will be consistent for all participants without an event.

A sensitivity analysis will use Bayesian methods to estimate the secondary all-cause mortality outcome treatment effect posterior distribution. These analyses will be performed in an analogous manner as the Bayesian analysis of the primary outcome (section 3.2.2).

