1.1 Study Design

The Trial to Assess Chelation Therapy 2 (TACT2) is a randomized, double blinded, placebo-controlled 2x2 factorial clinical trial. The study treatments are edetate disodium-based chelation (weekly infusion for 40 weeks) and high-dose oral multivitamins and multi-minerals (OMVM) (twice daily for up to 5 years). Subjects with diabetes mellitus with a prior myocardial infarction (MI) are recruited from participating sites in the US and Canada and randomized in a 1:1:1:1 fashion to 4 groups:

- i. Active chelation + active OMVM
- ii. Active chelation + placebo OMVM
- iii. Placebo chelation + active OMVM
- iv. Placebo chelation + placebo OMVM.

Patients will be followed for clinical events until the earlier of database lock or five years from randomization. Clinical outcomes will be collected by study sites at each infusion visit and by the DCRI Call Center at month 6 and 12, and every 4 months afterwards with the last assessment at month 60.

TACT2 is an event driven trial with a plan to continue until at least 282 primary endpoint events are identified. The original planned sample size was 1200 participants. The sample size was later modified to 1100. The final enrollment is 1000, but with an increased follow-up time to preserve statistical power. More details on sample size and power calculation are included later in the SAP.

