2.2 Data Sources

The data used for analysis will come from 5 sources: the randomization data from the Interactive Voice/Web System (IXRS), the e-CRF data collected by the iMedidata Rave electronic data capture system (RAVE), the adjudicated endpoint data from the clinical events committee database (CEC), the site-level information stored in the Clinical Trial Management System (CTMS) database, and the CDC National Death Index (NDI).

Masked-source NDI search results will be used to focus a search for supporting clinical and other documentation. If supporting documentation is obtained, the data will be submitted to the CEC process prior to being used in the analysis. If needed, a Mortality Review Committee will be assigned to classify potential death events when there are insufficient/incomplete or contradictory NDI and/or Call Center data to make a reliable determination. Additional details will be described in a separate charter.

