			If cause of death is unavailable in CEC and CRF, use NDI cause of death.	
Sensitivity Analysis of the Secondary All-Cause Mortality Outcome / Censor at the date of NDI assessment / mITT	*Same as secondary all-cause mortality analysis	*Same as secondary all-cause mortality analysis	*Same as secondary all-cause mortality analysis	Among subjects who are alive: Censoring date = max(date of NDI assessment, last known alive date) Date of NDI assessment is defined as: The last date that NDI results were assessed. This will be consistent for all participants without an event.

*See section 2.1 for the definition of ITT and mITT.

One participant who was randomized twice and received infusions from the second site will be censored at the second randomization. The other participant who was lost to follow-up at the first site and then was randomized at the second site will be censored at the time of lost to follow-up at the first site.

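### The NDI-date sensitivity analysis of all-cause mortality counts every participant without a recorded death as alive to an NDI-based date, with no exception for those who cannot be searched in the index

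*SAP*

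**What the plan says.** SAP 3.3.3 states that "participants with no event will be censored at the last date that NDI results were assessed", and then: "The censoring date will be consistent for all participants without an event". The corresponding row of Table 3 (SAP 3.1.1) reads "Censoring date = max(date of NDI assessment, last known alive date", that is, the later of the two dates. It defines the NDI date as follows: "The last date that NDI results were assessed. This will be consistent for all participants without an event". Neither place makes an exception by country, by success of linkage or by the period the index data cover, and neither gives a calendar date.

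SAP 1.1 says that participants "are recruited from participating sites in the US and Canada". SAP 2.2 lists five data sources, and the CDC National Death Index is the only death registry among them. It leaves further detail to a separate charter.

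The main all-cause mortality analysis works differently. Table 3 censors survivors at the date last known alive. The version in the testing hierarchy (SAP 3.2.1, step 2) is labelled as having conservative censoring.

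**The concern.** Censoring at a registry date rests on the idea that, had the person died by then, the registry would have shown it. That is true only for people the registry can find, and only up to the last date of death its data contain. For anyone else, the time between last contact and the registry date enters the denominator while a death in that time has little chance of entering the numerator.

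Two groups may be affected. The first is participants who cannot be searched: Canadians, if the US index does not hold Canadian deaths, and anyone without usable identifiers. The second depends on what *assessed* means. If it is the day the results were reviewed, every participant has a stretch after the data end in which the index could not show a death.

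At stake is the one mortality analysis meant to extend survivors' follow-up past last contact. It would understate mortality, and it would credit more false survival time to whichever arm lost more participants.

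**Working it through.** The plan states no figure for this analysis, so there is none to reproduce. The check has three parts.

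**1. Time the rule adds for participants who complete planned follow-up**

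Inputs from the documents:
- Enrolment ended December 31, 2020 (protocol section 3).
- The enrolment period is 3 years + 15 months = 4.25 years (SAP Appendix I).
- Follow-up is capped at 5 years (SAP 1.1).
- The administrative end is June 30, 2023 (SAP 2.4).
- Database lock is October 2023 (SAP Appendix I).

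Assumption: uniform enrolment.

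With entry time r between 0 and 4.25 years, June 30, 2023 falls at 6.75 years. Planned follow-up is F = min(5, 6.75 − r).
- Share reaching 5 years before the end: 1.75/4.25 = 41%.
- Mean F: (1.75 × 5 + 2.5 × 3.75)/4.25 = 4.26 years.
- Added time if the NDI date is June 30, 2023: (1.75²/2)/4.25 = 0.36 year on average, 1.75 at most.
- If it is about October 1, 2023: 0.36 + 0.25 = 0.61 year, 2.0 at most.
- If it is a data-through date such as December 31, 2022 (assumed): (1.25²/2)/4.25 = 0.18 year. For a searchable participant all of that lies within index coverage.

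Participants who withdraw or are lost gain more.

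**2. Effect on the mortality rate, no data lag**

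The documents give no loss rate by arm, no Canadian share and no mortality rate for this population, so these are assumptions. Take loss ℓ per year, an unsearchable share f, and an NDI date at 7.0 years.

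Mean contact time = (1 − E[e^(−ℓF)])/ℓ, where E[e^(−ℓF)] = [1.75·e^(−5ℓ) + (e^(−2.5ℓ) − e^(−5ℓ))/ℓ]/4.25.

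Mean time from randomization to the NDI date = 7.0 − 4.25/2 = 4.875 years.

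Ignoring deaths in the time totals, the understatement is about f × (4.875 − contact time)/4.875.

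| Loss/yr | Mean contact time (yr) | Share of time after contact | f = 5% | f = 25% |
|---|---|---|---|---|
| 3% | 3.99 | 18% | 0.9% | 4.5% |
| 5% | 3.83 | 21% | 1.1% | 5.4% |

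Simulation agrees. At 4 deaths per 100 patient-years and 3% loss, the rule gives 3.8–4.0 across f = 5–25%.

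With a lag between data end and NDI date (also assumed), the shortfall grows:
- f = 15%, 0.75-year lag: 3.64 against 4.02, 9% low.
- f = 25%, 1.5-year lag: 3.46 against 3.98, 13% low.
- f = 30%, 1.5-year lag, 5% loss, 3 deaths per 100 patient-years: 2.48 against 2.96, 16% low.

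**3. Effect on the hazard ratio**

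The common date is compared with censoring each participant at the last time a death could be found, on the same simulated data.

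| Loss/yr, chelation vs placebo | f | Lag (yr) | Common date | Capped | Shift |
|---|---|---|---|---|---|
| 5% vs 5% | 15–30% | 0–1.5 | – | – | within 0.002 |
| 3% vs 7% | 15% | 0 | 1.013 | 1.001 | 1.2% |
| 3% vs 6% | 15% | 0.75 | 1.015 | 0.999 | 1.6% |
| 3% vs 6% | 25% | 0.75 | 1.027 | 1.006 | 2.1% |
| 3% vs 7% | 30% | 1.5 | 0.730 | 0.698 | 4.6% |

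The first four rows include or use a true ratio of 1.00 and the last a true ratio of 0.70. Simulation noise is shared within a row, so only the comparison within a row is informative.

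For scale, about 150 deaths (1000 participants, 4 per 100 patient-years, about 4 years, less time lost to deaths) give SE(log HR) ≈ 2/√150 = 0.16. A 2% shift is about one-eighth of that.

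**The two texts side by side.** SAP 3.3.3 sets one date for all. Table 3 takes a maximum, which departs from a common date whenever someone is known alive after the NDI date, yet the same cell says the date is consistent for all. Both cannot hold as general rules.

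**The case against.** The strongest reply is that this is a labelled sensitivity analysis outside the test hierarchy, and that the main analysis already censors at last known alive. The main analysis counts index deaths found after last contact while giving survivors no time there, so it leans towards overstating mortality. A common-date version leans the other way, and the pair brackets the answer. This stands as a reason to rate the point as modest. It does not justify crediting registry follow-up to people the registry cannot find.

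Second, a reader might infer that the plan certainly runs past the index's data end. The documents do not support that. They mention no lag or cut-off, *assessed* is undefined, and the maximum in Table 3 has a purpose mainly if some last-alive dates fall after the NDI date, which fits a data-through date. On that reading only the coverage problem remains. Read literally, SAP 3.3.3 fits a review date. The point is therefore conditional.

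Third, a reader might infer that deaths could not be found in any of the added time. That is too strong. Sites and the Call Center can learn of deaths up to last contact in either country, US participants have index coverage for some or all of the rest, and SAP 3.3.2 refers to public data sources without limiting them to the NDI. No Canadian source is named, however.

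Fourth, the separate charter might settle coverage. As SAP 2.2 introduces it, the matter is how to classify deaths when NDI or Call Center data are incomplete or contradictory. The censoring rule itself is explicit in the SAP and carries no exception.

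**Conclusion.** The point holds in a limited form. The rule carries everyone without a recorded death to an NDI-based date, including participants who cannot be searched. The NDI date is undefined, and SAP 3.3.3 and Table 3 do not agree. That Canadian deaths fall outside the index is an inference from its name and agency, because the documents do not state its coverage.

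The likely effect is an understatement of mortality in both arms of up to about 5% with no lag and an assumed 5–25% Canadian share, and more if there is a lag. The hazard ratio is essentially unchanged when loss is equal by arm. With the assumed unequal loss it shifts by about 1–2%, well under one standard error, in favour of the arm losing more participants. Only the most extreme inputs tried (30% unsearchable, 1.5-year lag) gave 4–5%.

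A reader might conclude that the analysis cannot reassure about loss to follow-up at all. Shifts of this size do not support that. The change is still worth making, because unequal loss is when readers would turn to this analysis and the correction is small.

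**What to change.** In SAP 3.3.3 and the matching row of Table 3:
- Define the NDI date as the last date of death the search covers.
- Censor at the later of that date and last known alive only those participants without an event who were submitted to the NDI with sufficient identifiers.
- Censor all others, including Canadian participants, at last known alive.
- Delete the statement, in both places, that the date is the same for all participants without an event.

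This needs a few sentences and one flag for whether a participant was searchable, with no new data collection. The cost is that participants no longer share one closing date and total follow-up is slightly shorter.
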